7.5.2. Sensitivity Analyses of the Primary Efficacy Results

Several sensitivity analyses are planned:

1. Time to first STI using Kaplan-Meier and Cox PH regression.

2. Including all STIs diagnosed, irrespective of timing. The primary outcome will be modified to include any STI re-diagnosed within 28 days of the scheduled quarterly visits, and the statistical analysis for the primary analysis repeated.
3. Analysis counting each separate STI diagnosis as an event. A Poisson model fitted using GEE methods to account for multiple events from each participant will be used to estimate the change in rate of infections between arms. If necessary, to achieve a better fit, a zero-inflated Poisson model may be used.

7.5.3. Analyses of the Primary Efficacy Results while on study drug (Per protocol)

For the per-protocol analysis, for each cohort the doxycycline PEP arm will be restricted to study time prior to the first permanent discontinuation of study drug by self-report or documented on the study CRFs.

First discontinuation is defined as first of

- Product discontinuation
- Missed quarterly visit

Descriptive: Occurrence and reasons for first discontinuation will be tabulated (number of participants).

Analysis: The evaluation of the impact of non-disrupted use of doxycycline on any STI will use the same model as specified for the primary analysis, but also potentially adjusted for age, race/ethnicity, baseline STI, and baseline and follow-up sexual risk (number of partners, unprotected anal sex, employment). For the HIV negative cohort, PrEP at baseline; for the HIV positive cohort, viral suppression at baseline will also be considered.

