Doxycycline will be dispensed at each 3-month visit or in shorter intervals per patient preference, with additional dispensation as needed to replace lost medication or provide additional medication when needed (see MOPS for addition dispensing guidance). Capsules should be stored at room temperature (59-86° F) to the extent feasible. Participants will be instructed to take 200 mg of doxycycline within 24 hours after condomless sexual contact, and no later than 72 hours after sex. Condomless sexual contact is defined as receptive anal, insertive anal, vaginal, or oral sex (which includes oral/anal and oral/genital contact) or use of shared sex toys without a condom used for the entire time. For participants reporting multiple sexual encounters, 200 mg of doxycycline will be recommended to be taken every 24 hours until after the last sexual encounter. Participants will be instructed not to exceed 200 mg of doxycycline in a 24 hour period. Study staff will instruct participants on procedures for replacement of lost medication.

Doxycycline may be taken on an empty stomach or with food, and it is advised to take each dose with a large glass of water at least 60 minutes before bed to reduce risk of esophageal irritation. All participants randomized to PEP will be advised to avoid excessive sun exposure and artificial UV light, such as tanning beds, and to consider use of sunscreen if they will be exposed to sun.

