6.2 Study visits

Specific study procedures are detailed in Table 6.1. Visits will take place at enrollment and quarterly thereafter, up to 12 months. Interim visits may be scheduled for diagnosis and treatment of STI and collection of additional specimens or for evaluation of possible doxycycline associated adverse events. Participants may also request interim STI testing.

6.2.1 Enrollment Visit After confirming eligibility through pre-screening and prior to study procedures, we will obtain written informed consent and collect locating information; the latter will be updated at each study visit. At enrollment, demographic, behavioral, and clinical information will be collected and a release of information obtained to permit access to medical records. STI testing for chlamydia and gonorrhea through nucleic acid amplification testing (NAAT) of clinician or self-collected pharyngeal and rectal swabs and first void urine will be conducted. Serologic testing for syphilis will be conducted. If required STI testing has been conducted within past 30 days, these results may be used for the enrollment evaluation. Participants diagnosed with an STI at baseline will be treated; presence of a baseline STI will not preclude enrollment but STI's present at time of enrollment will not count towards study endpoints. All STIs will be reported to the local health department as required per local standard procedures.

Randomization Within 14 days of enrollment, participants will be randomized in a 2:1 ratio to openlabel doxycycline PEP or the standard of care control condition (regular STI counseling, screening and treatment as indicated). The randomization code and resulting allocation list will be generated and maintained by the study statistician. The list will be blocked and stratified by site. While neither participants nor study staff will be blind to each participant's randomization group once assigned, the randomization scheme will utilize varying block sizes in order to protect the blind prior to randomization of each participant.

- 6.2.2 Quarterly visits after enrollment. Quarterly visits will be conducted every 90 days, +2 weeks/ -10 weeks. Participants unable to attend a quarterly visit will be asked to return for an unscheduled visit as soon as feasible. The quarterly evaluations should be completed at the time of this visit. Subsequent visits should occur on the assigned quarterly scheduled to the extent possible.

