10 STATISTICAL CONSIDERATIONS

10.1 Outcome measures

10.1.1 Primary outcome:

Combined incidence of GC, CT, or early syphilis infection by laboratory- based diagnosis (e.g., positive GC or CT based on NAAT, syphilis based on four-fold increase in non- treponemal titers or positive darkfield on exudate from a lesion). Incident STI diagnoses will be ascertained through the study through periodic testing, interim visits for STI symptoms, as well as STI surveillance from the San Francisco and King County Departments of Health and by medical records provided for participants who receive their care from other clinical sites.

10.1.2 Secondary outcomes:

- Safety of doxycycline PEP, measured by evaluation of all Grade 3 and 4 AEs attributed to study medication.
- Tolerability, measured using a brief quarterly questionnaire administered to both intervention and control groups evaluating side effects commonly associated with doxycycline as well as recording any discontinuations of doxycycline by participants and their reasons.
- Acceptability, assessed through a brief questionnaire for all PEP recipients administered at month 6 and 12 and in-depth structured qualitative interviews for a subset, conducted within 6 months of month 12 visit. A separate consent will be provided for the in-depth qualitative interview at the time of this interview.
- Doxycycline coverage of sexual contacts in the prior 3 months, ascertained by sexual behavior and doxycycline

use from the web-based app, augmented by quarterly adherence questionnaires and pill counts.

- Longitudinal exposure to doxcycyline will be assessed using hair collection, with a semiquantitive evaluation in the control arm (doxycycline present vs. absent) and in the PEP arm (doxycycline concentration high vs. low).
- Adherence to HIV medications as reflected in viral suppression among participants living with HIV, assessed by chart review of HIV RNA levels conducted as standard clinical care.
- Discontinuation of PrEP, based on self-report
- Residual hair samples of participants without HIV infection on PrEP will be archived for future tenofovir testing to measure adherence to Truvada PrEP.

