7.5. Analysis of the Primary Efficacy Endpoint

7.5.1. Primary Efficacy Analysis

The primary analysis of efficacy will be conducted in the ITT cohort.

Endpoint definitions:

Primary endpoint: **Any STI** in the first, second, third or fourth quarter of follow-up, detected in post-baseline testing up to and including STI testing at months 3, 6, 9 and 12. Any STI diagnosed within 28 days of the same STI present at a quarterly visit will not be defined as an incident infection (suggesting incomplete treatment or persistent NAAT positivity without active infection, rather than re-infection). Incident infections detected and treated at interim visits after 28 days will be defined as incident infections for the current quarter. To avoid potential assessment bias, these will be handled in the analysis as if they would have been detected at a scheduled visit (months 3, 6, 9, and 12). Therefore, an STI diagnosed at 40 days after the month 6 visit will be carried forward as a primary event at the next scheduled visit (month 9). If a participant has more than one positive STI (either of the same or different bacterial infections at a scheduled visit) it will be counted as one primary event for that quarter. If scheduled visits are missed, infections will be assigned to the next scheduled visit.

All endpoints will be reviewed by the endpoint adjudication committee, blinded to doxycycline PEP assignment, for final determination, using most current CDC STI guidelines.

The criteria for an incident syphilis case will include a four-fold increase in non-treponemal titers (e.g., the RPR) and/or a consistent clinical presentation (e.g., characteristic chancre in primary syphilis which would be confirmed by a darkfield or reactive RPR without the requirement for a four-fold increase in titer).

Descriptive analysis

- The number of participants with any bacterial STI, and with each type of STI, will be summarized at each scheduled visit by arm.
- The number of STIs reported by each participant will be summarized at each scheduled visit by arm.
- For CT and GC, the anatomical site of infections will be detailed.

Statistical analysis

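### The per-protocol analysis cuts only the doxycycline arm at a missed quarterly visit, so its RR can leave the ITT RR for reasons unrelated to drug use

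*SAP*

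**What the plan says.** SAP 7.5.3 is the analysis of the primary endpoint while on study drug. In it, "the doxycycline PEP arm will be restricted to study time prior to the first permanent discontinuation of study drug". The section then defines first discontinuation as the earlier of two events: product discontinuation, and "Missed quarterly visit". No restriction is stated for the control arm. The model is that of the primary analysis, with optional covariates that include sexual risk during follow-up. The stated target is "The evaluation of the impact of non-disrupted use of doxycycline on any STI".

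Other sections bear on what a missed visit means:

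- **SAP 7.5.1** (primary analysis): "If scheduled visits are missed, infections will be assigned to the next scheduled visit".
- **Protocol 10.1.1:** infections are also ascertained outside study visits, "as well as STI surveillance from the San Francisco and King County Departments of Health".
- **Protocol 6.2.2:** "Participants unable to attend a quarterly visit will be asked to return for an unscheduled visit as soon as feasible", and "The quarterly evaluations should be completed at the time of this visit".
- **Protocol 5.3:** "Doxycycline will be dispensed at each 3-month visit or in shorter intervals per patient preference, with additional dispensation as needed". Protocol 1.2.7 also allows shipment to the home.
- **Protocol 9.1** lists five reasons for stopping study treatment, repeated in SAP 8.1.3. A missed visit is not among them.
- **Protocol 6.3.8 and SAP 2.2.2.2** record interruptions of 7 days or more directly, including those caused by having no doxycycline.

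**The concern.** The section contradicts itself. Its first sentence refers to a permanent stop of study drug, but its definition adds an event that is neither permanent nor a drug stop. That event can happen in either arm, and only one arm is cut when it does.

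Two mechanisms can then separate the per-protocol RR from the ITT RR even if nobody changes drug use:

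1. **Selection.** If attendance is related to STI risk, people who miss a visit lose their later time in the doxycycline arm but keep it in control. The shift goes one way if high-risk people miss more and the other way if low-risk people do.
2. **Carry-forward.** An infection from a missed quarter is counted at the next visit in control. In the doxycycline arm that next visit lies after the cut. This lowers the RR even when misses are random.

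Readers will attribute a gap between this RR and the ITT RR to drug use, and nothing planned would separate an attendance artefact from a drug effect. Nor is it stated whether a visit made up late counts as missed, so two programmers could build different datasets.

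A lesser point: the optional adjustment for follow-up sexual risk uses a variable measured after open-label randomisation, which doxycycline itself could affect.

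**Working it through.** **Inputs from the documents (SAP 3.3.1):** control risk 10% per quarter, doxycycline 5%, ICC 0.2, four visits, 130 control and 260 doxycycline participants per cohort, 10% annual loss to follow-up. The plan gives no figure for the per-protocol analysis. Its 80% power does reproduce from these inputs. With 123 evaluable controls (Protocol Table 10.2.2) and variance factor (1 + 3 × 0.2)/4 = 0.4, the effective control n is 123/0.4 = 307.5, and a pooled two-proportion test gives 79.5%.

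**Assumptions:** the documents give no rate of missing a visit and returning. Three rates per quarter are used: 2.6% (= 1 − 0.9^0.25, which treats all of the 10% annual loss as people who miss and return), 5% and 10%. Misses are random, or three times as common in the top or the bottom risk quartile. A share f of missed-quarter infections (0, 0.5 or 1) is carried to the next attended visit. Personal quarterly risk follows Beta(0.4, 3.6), which has mean 0.10 and ICC 0.2. Nobody stops the drug.

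**Hand check: random misses at rate m = 0.10, full carry-forward, true RR 1.00.** Under this Beta, the chance of at least one infection over 1, 2, 3 or 4 quarters is 0.100, 0.172, 0.2272 and 0.2714. An attended visit that follows j missed ones has the chance for j + 1 quarters. Averaged over the four visits, the share with

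- j = 1 is (0 + 0.10 + 0.09 + 0.09)/4 = 0.07;
- j = 2 is (0.01 + 0.009)/4 = 0.00475;
- j = 3 is 0.001/4 = 0.00025.

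Control rate = 0.100 + 0.07 × 0.072 + 0.00475 × 0.1272 + 0.00025 × 0.1714 = 0.1057. The doxycycline arm, cut at the first miss, has no carried-forward infections, so its rate is 0.100. RR = 0.100/0.1057 = 0.946. With a true RR of 0.50 it is 0.050/0.1057 = 0.473.

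**All patterns, equal misses by arm, rule as written** (exact enumeration of the 16 attendance sequences over the Beta distribution):

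| Missed per quarter | True RR 1.00 | True RR 0.50 |
|---|---|---|
| 2.6% | 0.95–1.01 | 0.48–0.51 |
| 5% | 0.91–1.02 | 0.46–0.51 |
| 10% | 0.83–1.04 | 0.42–0.52 |

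The low ends are the top quartile missing more with full carry-forward. The high ends are the bottom quartile missing more with none. Cutting both arms returns the true RR in every row. If half the misses at 2.6% are permanent, the range at true RR 1.00 is 0.98–1.01. If all are permanent, and no infection is counted after the last attended visit, it is 1.00.

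**Scale.** Var(log RR) = 1.6 × [0.9/(4 × 130 × 0.10) + 0.95/(4 × 260 × 0.05)] = 0.0277 + 0.0292 = 0.0569, so SE = 0.24. ln(0.50/0.48) = 0.041, or about 0.2 SE.

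**Unequal misses, true RR 1.00** (doxycycline at half or 1.5 times the control rate):

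| Control / doxycycline missed | As written | Both arms cut | Neither cut |
|---|---|---|---|
| 2.6% / 1.3% or 3.9% | 0.93–1.02 | 0.98–1.02 | 0.99–1.01 |
| 10% / 5% or 15% | 0.76–1.08 | 0.91–1.09 | 0.955–1.04 |

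The both-arm cut is not always the better rule. With control at 10% and the top quartile missing more, it gives 1.09 if doxycycline misses 5% (as written 0.91–0.99) and 0.91 if doxycycline misses 15% (as written 0.76–0.83).

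**Follow-up adjustment, true RR 0.50, risk proportional to partner numbers:** 0.50/1.1 = 0.45 if partners are 10% higher on doxycycline, 0.50/0.9 = 0.56 if 10% lower, and 0.50 if they do not differ.

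**The case against.** The strongest defence is that the rule fits its target. The analysis concerns uninterrupted use of doxycycline, control participants have no study drug to interrupt, and pills are dispensed at quarterly visits, so a missed visit is a plausible sign of a supply gap. That purpose is real. But attendance is not drug use, the protocol allows other supply routes, and interruptions are recorded directly.

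Other points have weight:

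- **Size.** Only the 2.6% rate has any anchor, and that anchor is loss to follow-up, not missing and returning. Read as permanent loss, it gives no shift. At 10% per quarter about a third of participants would miss at least one visit in the year (1 − 0.9^4 = 34% if random), while Protocol 4.3 reports annual retention above 80–90% at these sites. The larger shifts are possibilities, not forecasts.
- **Visit window.** Protocol 6.2.2 allows +2/−10 weeks, which goes far to define an attended visit. It does not say how a later make-up visit is classed.
- **Infections before the cut.** An infection found at an interim visit before the missed visit's date could reasonably be kept in the doxycycline arm. The model drops it and so may overstate the carry-forward effect.
- **Existing tables.** SAP 7.5.3 tabulates reasons for first discontinuation and SAP 6.1 gives retention by arm. These show how many visits were missed but do not correct the RR.
- **Follow-up adjustment.** It is optional, and the earlier trial described in Protocol 1.1 saw no difference in sexual behaviour between arms.

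None of this removes the asymmetry.

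**Conclusion.** The concern holds and is minor. As written, SAP 7.5.3 applies an attendance rule to one arm only, so the per-protocol RR can move with attendance and carry-forward alone. The direction is not fixed. At the one rate tied to a documented figure (2.6% per quarter, everyone returning), a true RR of 0.50 would read 0.48–0.51. Larger shifts need 5–10% missed per quarter, and the largest also need misses related to risk or differing by arm; the documents neither support nor exclude these. Surveillance infections counted in control after permanent dropout would add to the asymmetry. Confidence in the size is only medium, because the missed-visit rate, its link to risk and the carry-forward share are all assumed.

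**What to change.** In SAP 7.5.3:

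1. Apply the missed-visit cut to both arms, and keep product discontinuation as the only arm-specific rule.
2. Report beside it a version with no missed-visit cut in either arm, using the handling in SAP 7.5.1. State that the both-arm cut removes the bias only if missingness is similar by arm.
3. Define a missed visit, saying whether a late make-up visit counts as attended, and reconcile this with the reference to permanent discontinuation.
4. Add two entries to the discontinuation table: first missed visits in control, and recorded interruptions of 7 days or more among doxycycline participants who missed a visit.
5. Make adjustment for baseline covariates only the main adjusted version.

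**Cost.** SAP wording, which SAP 1 allows to change before database lock, and one extra model run. The both-arm cut also discards control visits. Of 130 × 4 = 520 per cohort, with random misses, those used fall from 520(1 − m) to 130 × Σ(1 − m)^k, k = 1 to 4: from 507 to 487 at 2.6%, 494 to 458 at 5% and 468 to 402 at 10%. The no-cut version keeps every attended visit but also any time off drug. If every missed visit left the next quarter unprotected, a true RR of 0.50 would read 0.51–0.52, 0.51–0.53 and 0.525–0.56 at those rates. Each version has a different weakness, so both should be shown.

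### If the per-protocol cut follows the carried-forward visit, infections diagnosed on doxycycline shortly before a stop are removed, in the doxycycline arm only

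*SAP*

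**What the plan says.** SAP 7.5.3 defines the per-protocol analysis by a cut in one arm: "the doxycycline PEP arm will be restricted to study time prior to the first permanent discontinuation of study drug". It takes first discontinuation as the earlier of product discontinuation and "Missed quarterly visit". The analysis "will use the same model as specified for the primary analysis", with possible extra covariates.

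That model (SAP 7.5.1, statistical analysis) has one record per participant at each of months 3, 6, 9 and 12. The endpoint definitions in the same section fix how infections found between visits enter it:

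- They are "defined as incident infections for the current quarter", and "these will be handled in the analysis as if they would have been detected at a scheduled visit". The stated purpose is to avoid assessment bias.
- In the SAP's example, "an STI diagnosed at 40 days after the month 6 visit will be carried forward as a primary event at the next scheduled visit", that is, month 9.
- "If scheduled visits are missed, infections will be assigned to the next scheduled visit".

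The primary analysis is separate from the cut: "The primary analysis of efficacy will be conducted in the ITT cohort". Under Protocol 9.1, participants who stop doxycycline stay in follow-up, so records after the stop should exist.

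**The concern.** The cut works on study time and the outcome works on scheduled visits. Take the SAP's example and add a permanent stop 60 days after month 6. The infection at day 40 was diagnosed on drug, 20 days before the stop, but its analysis time is month 9, after the cut. If the month 9 record is removed, so is the infection. A control participant with the same infection keeps it.

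The missed-visit trigger has the same effect without any decision to stop. An interim infection in a quarter that ends in a missed visit moves to the following visit, which always lies after the discontinuation that the missed visit itself defines. In the control arm it is carried forward and counted.

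At stake is the planned estimate of the effect of uninterrupted use. An analysis that can discard on-drug failures from one arm does not measure that cleanly, yet it would be read as support for the ITT result.

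**Working it through.** **1. The plan's own figure.** Inputs from SAP 3.3.1: 10% against 5% per quarter, four visits, ICC 0.2, 370 evaluable per cohort at 2:1 (about 123 control, 246 doxycycline; Protocol Table 10.2.2).

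- Effective n per arm = n × 4 / (1 + 3 × 0.2): 123 × 4 / 1.6 = 307.5 and 246 × 4 / 1.6 = 615.
- Pooled proportion = (0.10 + 2 × 0.05) / 3 = 0.0667.
- z = [0.05 × √307.5 − 1.96 × √(0.0667 × 0.9333 × 1.5)] / √(0.09 + 0.0475/2) = (0.877 − 0.599) / 0.337 = 0.82.
- Power is 79.5%, against the stated 80%.
- Annual risks: 1 − 0.9⁴ = 34.4% and 1 − 0.95⁴ = 18.5%, matching 34% and 19%.

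The planning inputs are therefore sound, and the true relative risk (RR) in what follows is 0.05 / 0.10 = 0.50.

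**2. One quarter, cut by assigned visit.** Let p = 0.05, f the share of infections found at interim visits, and h the share of those followed by a stop before the next visit. The documents give neither f nor h; both are assumptions.

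- Stopping unrelated to infection, with probability s: retained risk = p(1 − s) / (1 − s) = p, so RR = 0.50. Infections are lost, but the whole quarter leaves the denominator with them.
- Stopping after infection: retained risk = p(1 − fh) / (1 − pfh). With f = 0.4 and h = 0.2: 0.05 × 0.92 / 0.996 = 0.0462, so RR = 0.46.

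**3. Four quarters.** Beta-binomial simulation with ICC 0.2, 246,000 doxycycline and 124,000 control participants, and an assumed 2% of unrelated stops per quarter. Repeat runs agreed to within about 0.005.

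| f | h | RR, cut by assigned visit | RR, stop quarter kept |
|---|---|---|---|
| 0.2 | 0 | 0.496 | 0.495 |
| 0.2 | 0.02 | 0.497 | – |
| 0.2 | 0.05 | 0.494 | – |
| 0.2 | 0.10 | 0.488 | 0.498 |
| 0.2 | 0.20 | 0.478 | 0.497 |
| 0.2 | 0.30 | 0.462 | 0.490 |
| 0.4 | 0 | 0.500 | 0.500 |
| 0.4 | 0.02 | 0.494 | – |
| 0.4 | 0.05 | 0.487 | – |
| 0.4 | 0.10 | 0.480 | 0.499 |
| 0.4 | 0.20 | 0.449 | 0.485 |
| 0.4 | 0.30 | 0.431 | 0.487 |

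At f = 0.4, h = 0.2, RR is 0.449 with the cut and 0.485 with the stop quarter kept. The step from 0.485 to 0.449 is due to the rule. The step from 0.50 to 0.485 arises, apart from simulation noise, because participants who stop after infection leave later quarters, as with any on-treatment censoring.

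**4. Infections per cohort.** At f = 0.4, h = 0.2, expected losses from infection-driven stops are 246 × 4 × 0.05 × 0.4 × 0.2 = 3.9 of 246 × 4 × 0.05 = 49.2.

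A second simulation used 260 doxycycline participants and included missed visits:

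- Unrelated stopping, 7% stops and 10% missed visits: 0.2 to 0.8 of about 47 on-drug infections lost, for f from 10 to 50%.
- Unrelated stopping, 15% stops and 20% missed visits: 0.3 to 1.5 of about 42 lost. RR stays at 0.50 in both cases.
- At the far corner, f = h = 0.5, about 12 are lost and RR reads 0.38.

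**5. The denominator.** If the infection is dropped but the part-quarter stays in as event-free, RR is about 0.45-0.48 even with unrelated stopping. If events are counted by diagnosis date over full-quarter records, no on-drug infection is lost, but RR is about 0.46-0.49, because the denominator no longer matches the events.

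**The case against.** The strongest reply is that the SAP never says the assigned visit decides on-drug status. An infection at day 40 lies in study time before a stop at day 60, and the carry-forward rule exists to avoid assessment bias between arms. Under a diagnosis-date reading no on-drug infection is lost. That stands, so the loss is conditional. But the reused model has only visit-dated outcomes, and the diagnosis-date reading leaves the part-quarter denominator open. Text is needed either way.

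A reader might also infer that stops are enriched for doxycycline failures, so that the analysis must overstate effectiveness. The documents do not support this. Protocol 9.1 allows a stop at the participant's request but does not mention infection. The only stopping figure, 8 participants (7%) in the earlier French trial (Protocol 1.2.1), concerns side effects. Protocol 6.6 has PEP held during doxycycline treatment of an STI and then resumed, so treatment alone is not a permanent stop. Stopping after a breakthrough infection is plausible in an open-label trial, but it is an assumption. Values of h of 10-30% are 5 to 15 times the assumed 2% background; at 2-5% the shift is at most about 0.01.

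Finally, SAP 7.5.3 tabulates reasons for first discontinuation, so infection-driven stopping could be visible. That helps interpretation but does not restore the lost records.

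**Conclusion.** The point holds in conditional form. The two rules, applied together in the natural way, can remove on-drug infections from the doxycycline arm only, through a product stop or a missed visit. Only interim infections in the quarter of the stop or missed visit are exposed; infections found at scheduled visits before the stop are kept.

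With stopping unrelated to infection and whole quarters removed, there is no bias. If stopping follows infection, the per-protocol RR moves in favour of doxycycline: from a true 0.50 to about 0.49-0.50 at h of 2-5%, and to about 0.43-0.49 at 10-30%, for f of 20-40%. Those ranges rest on assumed f, h and background stopping.

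It would be wrong to infer that the main result is inflated. The primary analysis is ITT, the cut does not touch it, and no power figure changes. The change is worth making before the per-protocol estimate is used, but it is not a threat to the trial's primary conclusion.

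**What to change.** In SAP 7.5.3, state that:

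1. Doxycycline-arm quarters that begin after the date of permanent discontinuation are excluded. The quarter in which doxycycline is stopped is kept whole, with its infections and its denominator record.
2. An interim infection in a quarter that ends in a missed visit is counted in that quarter for this analysis, and the missed-visit rule applies in the same way to both arms. The text should also say how such a quarter is recorded when there was no interim diagnosis, so that these quarters do not enter only when positive.

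Sorting infections by specimen date instead should not be adopted unless a matching part-quarter denominator is specified, for the reason in step 5 of the working.

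The cost is two or three sentences; SAP section 1 allows revision until database lock, and no new data are needed. One downside is that some off-drug days stay in the stop quarter. The other is that the small selection effect remains (RR about 0.48-0.50 in these scenarios), because participants who stop after infection leave later quarters. The report should say so.
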